#### PROTOCOL SYNOPSIS

#### Name of Sponsor/Company:

Denovo Biopharma LLC [name] [name] USA

Name of Investigational Product: Liafensine (DB104; previously BMS-820836)

Name of Active Ingredient: Liafensine

**Protocol Number: DB104-01** 

Title of Study: A Biomarker-Guided, Randomized, Double-Blind, Placebo-Controlled Efficacy and

Safety Study of Liafensine in Patients with Treatment-Resistant Depression

**Study Center(s):** Multiple

**Phase of Development:** 2b

#### **Rationale:**

Major depressive disorder (MDD) is a common psychiatric disorder, with a lifetime prevalence rate of approximately 13-17% in the United States (Hasin 2005, Kessler 2005). Although options for pharmacologic treatment have expanded significantly in the past 25 years, between one-third and two-thirds of patients will not respond to the first antidepressant prescribed, and up to 33% will not respond to multiple interventions (American Psychiatric Association 2013, Berlim 2008, Cain 2007). Novel antidepressants that produce a clinically significant improvement in patients with MDD who have failed to respond to more than one treatment of adequate dose and duration, without producing significant side effects, would represent an important advance in the treatment of treatment-resistant depression (TRD).

For most of the last 30 years, the biogenic amine hypothesis of depression has been driving much of the research into the etiology and treatment of this debilitating psychiatric disorder. Most conventional antidepressants are antagonists at serotonin (5-HT) and/or norepinephrine reuptake sites, and their efficacy correlates reasonably well with their affinity for these receptors. At present, the most commonly used treatments for MDD are the selective serotonin reuptake inhibitors (SSRIs), such as escitalopram, or the serotonin-norepinephrine reuptake inhibitors (SNRIs), such as duloxetine. Recently, a compound with a novel mechanism of action, esketamine (SPRAVATO®), was approved in the United States (US) for the treatment of TRD in conjunction with an oral antidepressant (SPRAVATO 2019). While the precise mechanism of action of esketamine is unknown, the compound is an N-methyl-D-aspartate (NMDA) receptor antagonist. Esketamine use is associated with significant adverse effects including dizziness, nausea, sedation, and psychological effects, including dissociative/perceptual changes. Because of the risks of dissociation with esketamine, the US Food and Drug Administration (FDA) has established a Risk Evaluation and Mitigation Strategy (REMS) requiring that patients be monitored by a healthcare professional for at least 2 hours at each treatment session, concluding with an assessment establishing that the patient is clinically stable and may safely leave the healthcare setting.

This adverse event profile, together with esketamine's REMS requirements, limits its clinical utility, and supports the continued development of novel compounds for the treatment of TRD.

Liafensine (also known as DB104 and previously BMS-820836) is 6-[(4S)-1,2,3,4-tetrahydro-2-methyl-4-(2-naphthalenyl)-7-isoquinolinyl]-3-pyridazinamine and it is a potent and selective inhibitor of the reuptake of the 3 monoamines: 5-HT, norepinephrine, and dopamine. Liafensine was developed to incrementally advance antidepressant treatment by synergizing these individual monoaminergic approaches to treating depression.

Liafensine has been tested in 11 Phase 1 studies, and 3 Phase 2b studies (including one rollover study). In the Phase 1 studies, single doses of up to 5 mg, and multiple doses of up to 4 mg liafensine were found to be generally safe and well tolerated. The pharmacokinetic (PK) profile of liafensine was compatible with once-daily (OD) dosing, supporting the potential for liafensine to have low potential for discontinuation symptoms. In the Phase 2b studies, patients who did not experience adequate response to either duloxetine (Study CN162006), or duloxetine or escitalopram (Study CN162007), were randomized to receive either liafensine or duloxetine (CN162006), or duloxetine or escitalopram (CN162007), for 6 weeks. In Study CN162006, a flexible dose of liafensine was used (0.5-2 mg QD). In Study CN162007, several fixed dosage levels of liafensine were used (0.25, 0.5, 1, and 2 mg OD). In these Phase 2b studies, liafensine was found to be generally safe and well tolerated. In Study CN162006, the most common adverse events (AEs) reported by at least 5% of patients treated with liafensine were headache (7.0%), nausea (7.0%), constipation (5.3%), and anxiety (5.3%). In Study CN162007, the most common AEs reported by at least 5% of patients treated with any dose of liafensine were headache (14.3%), nausea (12.0%), nasopharyngitis (8.8%), upper respiratory tract infection (8.0%), dry mouth (8.0%), constipation (7.7%), dizziness (7.0%), diarrhea (5.5%), fatigue (5.9%), and urinary tract infection (5.5%).

In the Phase 2b studies conducted by Bristol-Myers Squibb (BMS), there were no significant differences noted between the treatment groups in the decrease (improvement) of the mean Montgomery-Åsberg Depression Rating Scale (MADRS) total score. In an effort to identify a potential pharmacogenomic biomarker of response to liafensine, Denovo Biopharma LLC (Denovo) has conducted a genome-wide scan with human whole genome single nucleotide polymorphism (SNP) arrays using germline deoxyribonucleic acid (DNA) extracted from blood samples of patients in BMS Studies CN162006 and CN162007. From this genome-wide screening, SNP rs12217173 was identified as strongly associated with treatment response to liafensine (p =  $6.6 \times 10^{-8}$ ). Patients with a GG genotype at rs12217173 showed significantly better response to liafensine compared to patients with an AA or AG genotype, or patients in the control arm (duloxetine or escitalopram). These findings were replicated using a separate validation sample set. Liafensine treatment effects in patients with the GG genotype were comparable for the 0.5 to 2 mg QD flexible doses in the CN162006 study and for the 1 mg OD and 2 mg OD doses in the CN162007 study. These combined data showed that patients with the GG genotype had a 4.7-point difference in MADRS total score decrease from baseline in the liafensine arm vs the control arm (p = 0.025), while patients with the AA or AG genotype at rs12217173 did not show an improved treatment effect in the liafensine arm vs the control arm (MADRS 0.3-point difference, p = 0.74). Moreover, patients carrying different genotypes at rs12217173 did not exhibit different treatment responses to duloxetine or escitalopram. Thus, SNP rs12217173 appears to be a pharmacogenomic biomarker specific for liafensine: Denovo has termed rs12217173 as "DGM4" (Denovo Genomic Marker 4) and the GG genotype of DGM4 is defined as DGM4 positive, whereas the AA or AG genotype of DGM4 is defined as DGM4 negative.

#### **Objectives:**

# Primary Efficacy Objective

• To demonstrate that liafensine is superior to placebo in DGM4-positive patients with TRD as assessed by the change in MADRS total score from baseline to Day 42 of double-blind treatment

#### Key Secondary Efficacy Objective

• To evaluate the change from baseline to Day 42 in DGM4-positive patients with TRD treated with liafensine vs placebo on the Clinical Global Impressions Scale-Severity (CGI-S)

#### Safety Objectives

- To compare the safety and tolerability of liafensine vs placebo in all randomized patients with TRD who received at least one dose of study drug during double-blind treatment
- To evaluate safety for liafensine 1 mg QD and 2 mg QD vs placebo in both DGM4-positive and DGM4-negative patients

# Other Secondary Efficacy Objectives

- To evaluate the Clinical Global Impressions Scale-Improvement (CGI-I) at Day 42 in DGM4-positive patients with TRD treated with liafensine vs placebo
- To evaluate the change from baseline to Day 42 in DGM4-positive patients with TRD treated with liafensine vs placebo on the patient-reported functionality with Sheehan Disability Scale (SDS)

#### **Exploratory Objectives**

- To compare the proportion of DGM4-positive patients with TRD who respond to liafensine after 6 weeks of treatment vs placebo (response is defined as ≥ 50% improvement from baseline in MADRS total score at Day 42)
- To compare the proportion of DGM4-positive patients with TRD who are in remission after 6 weeks of treatment with liafensine vs placebo (remission is defined as MADRS total score ≤ 10 at Day 42)
- To evaluate the change from baseline to Day 42 in DGM4-positive patients with TRD treated with liafensine vs placebo on MADRS anhedonia subscale and individual items
- To compare the efficacy of liafensine vs placebo in DGM4-negative patients with TRD, as assessed by change in MADRS total score from baseline to Day 42
- To evaluate efficacy for liafensine 1 mg QD and 2 mg QD vs placebo in both DGM4-positive and DGM4-negative patients
- To evaluate the PK of liafensine as part of the population PK analyses

#### **Endpoints:**

# **Primary Endpoint**

• Change in MADRS total score from baseline to Day 42, in DGM4-positive patients

# **Key Secondary Endpoint**

• Change in CGI-S from baseline to Day 42, in DGM4-positive patients

#### Safety Endpoints

- Adverse events as characterized by type, frequency, severity, timing, seriousness, and relationship to study therapy
- Laboratory abnormalities as characterized by type, frequency, severity, and timing
- Vital signs including supine (after at least 5 min rest) and standing (after standing 1 min and 3 min), blood pressure and heart rate, weight, electrocardiogram (ECG), clinical laboratory evaluation, Discontinuation-Emergent Signs and Symptoms scale (DESS) scale, and Columbia Suicide Severity Rating Scale (C-SSRS) data

#### Other Secondary Endpoints

- CGI-I at Day 42, in DGM4-positive patients
- Change in SDS from baseline to Day 42, in DGM4-positive patients

# **Exploratory Endpoints**

- Treatment response (defined as ≥ 50% improvement from baseline in MADRS total score at Day 42) in DGM4-positive patients
- Remission (defined as MADRS total score  $\leq$  10 at Day 42) in DGM4-positive patients
- Change in MADRS anhedonia subscale and individual items from baseline to Day 42, in DGM4-positive patients
- Change in MADRS total score from baseline to Day 42, in DGM4-negative patients
- Change in MADRS total score from baseline to Day 42 in 1 mg QD group and 2 mg QD group, in both DGM4-positive and DGM4-negative patients

#### **Study Design:**

This study will be conducted as a multicenter, randomized, double-blind, placebo-controlled Phase 2b trial to assess the efficacy, safety, tolerability, and PK of liafensine in DGM4-stratified TRD patients. The study includes an up to 21-day screening period.

Approximately 180 patients with TRD who meet all eligibility criteria will be randomized in a 1:1:1 ratio to receive either liafensine 1 mg QD, liafensine 2 mg QD, or placebo QD for 6 weeks. Approximately 150 randomized patients carrying genotype GG at DGM4 (DGM4-positive) and approximately 30 randomized patients carrying genotype AA or AG at DGM4 (DGM4-negative) will be enrolled in this study. DGM4 status (positive vs negative) of randomized patients will be blinded to the sites, the patients, and sponsor. An Interactive Response Technology (IRT) system will be used for blinding DGM4 status, and to achieve the planned randomization ratio of DGM4-positive:DGM4-negative patients by randomly excluding most screened DGM4-negative patients (~80%). Randomization will be stratified by DGM4 status (positive vs negative) and region (North America vs Other). Patients who complete the study or discontinue after randomization will have two post-study follow-up visits (14 days after the last administered dose of study drug, and 28 days after the last administered dose of study drug); the 2nd follow-up visit will be conducted via phone call. Every effort will be made to ensure that the protocol-required tests and procedures are completed.

During the study, safety will be assessed on the basis of spontaneously reported AEs; the DESS; physical, neurological, and psychiatric examinations (including the C-SSRS); vital signs including supine and standing blood pressure and heart rate; weight; 12-lead ECGs; clinical laboratory test results; serum and urine pregnancy tests (females of childbearing potential only); and concomitant medication assessments. In addition to blood samples collected for PK, additional blood samples may be collected for determination of plasma concentrations of liafensine and its primary metabolite in association with the evaluation of safety signals.

The overall study design is shown in Figure 1. The schedule of study assessments is presented in Table 1 with the clinical laboratory tests shown in Table 3.

To ensure the safety of patients enrolled in this study, an Independent Data Monitoring Committee (IDMC) will monitor data on an ongoing basis. The IDMC will comprise individuals external to the sponsor and will consist of at least one medical expert in the relevant therapeutic area, at least one hepatologist, and at least one statistician.

#### Methodology:

This is a randomized, double-blind, placebo-controlled Phase 2b trial to assess the efficacy, safety, tolerability, and PK of liafensine. The primary endpoint is change in MADRS total score from baseline (Visit 3, Day -1) to Visit 7 (Day 42) in DGM4-positive patients. The primary analysis will be conducted to assess the superiority of liafensine treatment (combined liafensine 1 mg QD and 2 mg QD doses) vs placebo in randomized patients who are DGM4-positive.

#### **Sample Size Justification:**

Eligible patients will be randomized 1:1:1 to receive liafensine 1 mg QD, liafensine 2 mg QD, or placebo QD. The primary analysis is to assess treatment difference in MADRS total score change from baseline (Visit 3, Day -1) to Visit 7 (Day 42), between the combined liafensine 1 mg QD and 2 mg QD doses vs placebo, in DGM4-positive patients. A sample size of 47 randomized DGM4-positive patients per arm is sufficient to detect a 4.5-unit difference between the combined liafensine 1 mg QD and 2 mg QD treatment groups and the placebo treatment group in the change in MADRS total score with 80% power at the 2-sided 0.05 alpha level, assuming a standard deviation of 9 units.

To compensate for potential loss of power due to randomized patients who do not take at least one dose of study drug or who do not have a post-randomization efficacy evaluation (~5%), a total of approximately 150 DGM4-positive patients (50 DGM4-positive patients per arm) will be randomized.

To examine trend in the total patient population and in the subgroup of DGM4-negative patients in order to evaluate DGM4 as a potential biomarker for predicting response to liafensine, approximately 20% additional DGM4-negative patients (10 per arm, total approximately 30) will also be randomized. The sample size of 30 randomized patients in the DGM4-negative group is not estimated based on formal statistics in terms of power and alpha level.

Sample size re-estimation may be conducted if the percentage of missing data at Day 42 visit is higher than expected and/or if the observed variance is higher than the one assumed in the sample size estimation.

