## 4.1. Subject Inclusion Criteria

Patients must meet all the following inclusion criteria to be eligible for enrollment into the study:

- 1. Provide signed informed consent which includes pharmacogenomic (PGx) testing.
- 2. Have a diagnosis of MDD without psychotic features, according to the *Diagnostic and Statistical Manual of Mental Disorders*, 5th Edition (DSM-5) criteria, based on clinical assessment and confirmed by the Mini International Neuropsychiatric Interview (MINI).
- 3. TRD documented in the Massachusetts General Hospital (MGH) Antidepressant Treatment Response Questionnaire (ATRQ) (5-year version). That is:
  - a. clinically meaningful inadequate response (estimated < 50% improvement per investigator/patient consensus and documented by the investigator) with:
    - 1) at least 2 treatment courses with antidepressant regimens;
    - 2) used at least 2 different pharmacologic treatment classes (eg, SSRI, SNRI, TCA, MAOI, atypical); or if only one class treatment is used, at least one combination treatment course;
    - 3) the doses have been given at accepted therapeutic doses for an adequate duration (at least 6 weeks), per product label;
    - 4) One of these inadequate response must occur within the current episode.

**Note**: non-pharmacological treatment (eg, cognitive behavioral therapy, electroconvulsive therapy, repetitive transcranial magnetic stimulation, vagus nerve stimulation, acupuncture) are not counted as treatment regimen.

- 4. To be eligible, patients must have DGM4 genotype results obtained from the designated Clinical Laboratory Improvement Amendments (CLIA) lab, and all eligible DGM4-positive patients and about 20% DGM4-negative patients will be randomly included by an IRT system in order to achieve the appropriate randomization ratio of DGM4-positive vs negative patients.
- 5. Pregnancy conception limitations

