5.4. Efficacy Analysis

All analyses will be presented for DGM4-positive, DGM4-negative, and both DGM4-positive and DGM4-negative subjects.

The analyses of the primary and key secondary efficacy endpoints will be conducted on the FAS. Supportive sensitivity analyses will be performed in the per protocol analysis set for primary and key secondary efficacy endpoints unless otherwise specified.

5.4.1. Primary Endpoint: Change in MADRS Total Score from Baseline to Day 42, in DGM4-Positive Patients

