5.4.1.2. Main Estimator

The primary efficacy analysis will be performed in DGM4-positive patients at 1-sided significance level of 0.05 using MMRM with imputation based on the MAR assumption. The model will include the fixed effects of treatment, visit (categorical covariate), treatment-by visit interaction, treatment by baseline MADRS total score, baseline MADRS total score (continuous covariate), and region. Change from baseline in weekly visits at Days 7, 14, 28, and 42 will be

the repeated outcome measures, and the model will use an unstructured variance-covariance matrix. If the model does not converge the algorithm (Lu 2010) will be used to assist in the convergence.

The following hypothesis will be tested based on the test statistics from the mixed model:

 $H_0: u_i - u_0 = 0 \text{ vs. } H_A: u_i - u_0 \neq 0$

where u_i is the expected mean change from baseline in MADRS for liafensine at Day 42 and u_0 is the expected mean change from baseline in MADRS for placebo at Day 42. In H₀ and H_A above, i = 1, 2, 3 are for liafensine 1 mg, 2 mg, and both arms pooled, respectively, for implementing the closed testing procedure described in Section 3.7. The LSMESTIMATE statement in SAS Mixed procedure will be used to test the global null hypothesis of no treatment difference between both active arms and placebo while keeping all 3 treatment groups separately. Please see sample SAS code in Appendix 8.2.

The LS mean for change from baseline in MADRS total score at Day 42 for the combined liafensine treatment arms (1 mg QD and 2 mg QD) and placebo arm will be estimated from the MMRM model. The comparison of the change in MADRS total score from baseline to Day 42 between each of the two liafensine treatment arms and placebo will be carried out using the same approach. Separate figures with the mean change (\pm SD) and LS mean change (\pm SE) by visit will be displayed.

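### The combined DGM4-positive plus DGM4-negative efficacy result describes an enriched sample of about 83% positives and is not weighted back to the screened TRD population

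*Protocol*

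**What the plan says.** - **Sampling.** Protocol 4.1 (inclusion criterion 4) states that "all eligible DGM4-positive patients and about 20% DGM4-negative patients will be randomly included by an IRT system". Protocol 3.1 and 5.5 and SAP 2.1 describe the same step as random exclusion of about 80% of screened negatives.
- **Planned numbers.** The Synopsis sample size section states that "a total of approximately 150 DGM4-positive patients (50 DGM4-positive patients per arm) will be randomized" and that "approximately 20% additional DGM4-negative patients (10 per arm, total approximately 30) will also be randomized". The negative group is expressly not sized for power.
- **Purpose of the negatives.** The same section gives it as "To examine trend in the total patient population and in the subgroup of DGM4-negative patients in order to evaluate DGM4" as a marker of response. Protocol 3.4 and 8.2 and SAP 2.3 repeat this.
- **Combined presentation.** SAP 5.4: "All analyses will be presented for DGM4-positive, DGM4-negative, and both DGM4-positive and DGM4-negative subjects".
- **Model.** SAP 5.4.1.2: "The model will include the fixed effects of treatment, visit (categorical covariate), treatment-by visit interaction, treatment by baseline MADRS total score", plus baseline score and region. Neither this list nor the code in SAP 8.2 has a DGM4 term or a weight. SAP 3.6 says efficacy analyses are stratified by biomarker status and region, but no section standardises to the genotype mix of the screened patients.

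**The concern.** One stratum is kept whole and the other is thinned to about a fifth. A combined analysis that counts each randomised patient once therefore averages the treatment effect over roughly 83:17, a ratio set by the IRT rather than by any patient population. Adding DGM4 as a stratification factor or covariate does not change this. With 2:1 active-to-placebo allocation in both strata and similar variance, a common treatment effect is still weighted about 150:30.

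What is at stake is interpretation. The premise of the trial is a larger effect in positives. On that premise, a combined figure read as the trend in the total patient population is pulled towards the positive stratum, and it could suggest benefit irrespective of the marker. The negatives were enrolled to examine that very question.

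**Working it through.** **Inputs from the documents:** 150 positives (100 active, 50 placebo); 30 negatives (20 active, 10 placebo); planned effect 4.5 points; SD 9; negative sampling fraction about 0.20; 1-sided 0.05 for nominal tests (SAP 3.7).

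**Assumed inputs:** 0.3 points in negatives. This is the figure in Protocol 1.2.1, taken from trials against duloxetine or escitalopram, with its direction not clearly stated. The GG share p in the screened population is not given in the documents.

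**1. The plan's own figure.** With 2:1 pooled allocation, placebo n = 1.5 × [9 × (1.960 + 0.842) / 4.5]² = 47.1, which agrees with the stated 47 per arm. Then 47 / 0.95 = 49.5, or 50 per arm. The planning inputs reproduce.

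**2. Sample mix.** 150 / 180 = 83.3% positive.

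**3. Unweighted combined result.**
- Difference = (150 × 4.5 + 30 × 0.3) / 180 = 3.80.
- SE = 9 × √(1/120 + 1/60) = 1.42.

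**4. Weighted with the plan's stated fractions.** Positives get weight 1 and negatives 1 / 0.20 = 5, so p = 150 / (150 + 30 × 5) = 0.50.
- Stratum SEs: positives 9 × √(1/100 + 1/50) = 1.559; negatives 9 × √(1/20 + 1/10) = 3.486.
- Difference = 0.5 × 4.5 + 0.5 × 0.3 = 2.40.
- SE = √(0.25 × 1.559² + 0.25 × 3.486²) = 1.91, and 1.91 / 1.42 = 1.34.

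**5. Chance of nominal significance** (normal approximation). Unweighted: Φ(3.80/1.423 − 1.645) = Φ(1.03), about 85%. Weighted: Φ(2.40/1.909 − 1.645) = Φ(−0.39), about 35%.

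**6. Dependence on the GG share.** The gap between the two estimates is (0.833 − p) × (4.5 − 0.3).

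| Assumed GG share | Negatives screened per 150 positives | Fraction needed to reach 30 | Weighted difference | SE | SE relative to unweighted |
|---|---|---|---|---|---|
| 50% | 150 | 20% | 2.40 | 1.91 | 1.34 |
| 30% | 350 | 8.6% | 1.56 | 2.48 | 1.75 |
| 20% | 600 | 5% | 1.14 | 2.81 | 1.97 |

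The protocol uses 20% in two senses: added negatives relative to positives (30/150), and the fraction of negatives sampled. Both hold together only at a 50% GG share. At 30% or 20% GG, sampling one in five would bring in 70 or 120 negatives rather than 30.

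**7. Sensitivity to the effects.** With 4.5 points in both strata, both estimates are 4.5 and the gap is zero. If the 0.3 points favour control, the unweighted difference is (675 − 9) / 180 = 3.70, and the weighted one at 50% GG is 2.25 − 0.15 = 2.10.

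**The case against.** The strongest reply is that the plan never claims to estimate an effect in unselected patients. No objective or endpoint in Protocol 2 or SAP 1 concerns a combined population, and total patient population may simply mean all randomised patients. This stands in part: the phrase is ambiguous, and that is itself a reason to label the result.

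The result is also well contained. Primary and secondary conclusions rest on DGM4-positive patients. All efficacy comparisons outside the MADRS sequence in positives carry nominal p-values only (Protocol 8.3.3.1, SAP 3.7). SAP 5.4 presents the stratum results as well as the combined one. The positive-versus-negative comparison is planned descriptively with an optional interaction term (Protocol 8.3.3, SAP 5.6.5). All of this stands and keeps the point minor.

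The weighted estimate is imprecise. At 20% GG it puts 80% of the weight on about 30 patients and gives 1.14 with SE 2.81. That is a fair reason to keep it supportive and not to let it replace the unweighted result.

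A reader might infer three stronger things that the documents do not support:
- That the combined figure necessarily overstates the effect. It does so only if positives benefit more, which is what the negatives were added to explore.
- That it is 2.4 to 3.3 times too large (3.80/1.56 and 3.80/1.14). That range rests on an assumed 20–30% GG share, which does not fit 150:30 with 20% sampling.
- That a positive combined result would contradict the earlier all-comer Phase 2b trials. Those used active comparators; this trial uses placebo.

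**Conclusion.** The point holds conditionally and is minor. The combined result is planned, the sample is about 83% positive by construction, and nothing weights it back. Under the trial's own premise, the unweighted difference is higher than the effect in the screened TRD population. The illustrative gap is 1.4 points (3.8 against 2.4) at the 50% GG share implied by the plan's fractions. A lower GG share widens the gap, but it would also require a sampling fraction well below 20% to end with 30 negatives. These sizes rest on SD 9, on 4.5 points in positives, and on a 0.3-point effect in negatives borrowed from active-control trials. The primary analysis in DGM4-positive patients is not affected.

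**What to change.** In SAP 5.4:

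1. Label the unweighted combined result as describing the enriched randomised sample, and show it beside the positive and negative stratum estimates.
2. Add a supportive combined MADRS estimate: p × (difference in positives) + (1 − p) × (difference in negatives), with SE = √[p² × SE₊² + (1 − p)² × SE₋²].
3. Take p from the actual IRT inclusion records, weighting each stratum by the inverse of its realised inclusion probability rather than the nominal 20%. The genotype mix at Visit 1 gives the same weights only if later screen failure is similar by DGM4 status. That is plausible, since sites are blinded to status.
4. Say how the difference in negatives is obtained. SAP 5.6.4 limits negatives to descriptive statistics, whereas SAP 5.4 and Protocol 8.3.3 imply a modelled estimate.

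The cost is SAP wording and one extra estimate from counts the IRT should already hold. The downside to state in the SAP is a wider interval: SE about 34% larger at 50% GG and about double at 20%, driven by the roughly 30 negatives.
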